1.3. Sample Size and Power

The sample size in this study is determined based on practical considerations and empirical experience with similar types of studies. No sample size and power calculation were performed. Up to 25 participants will provide a preliminary assessment of descriptive safety, efficacy, and PK.

2. TYPE OF PLANNED ANALYSIS

2.1. Interim Analyses

Prior to the final analysis, interim analyses may be conducted, and the analyses may be submitted to regulatory agencies to seek guidance for the overall clinical development program.

2.1.1. Planned Internal Analyses

Two interim internal analyses are planned to be conducted:

- After all participants have completed their Day 133 visit (last scheduled study visit of Period 2), started Period 4A (if the ART restart criteria are met), or prematurely discontinued the study
- After all participants have completed the end-of-Period 3 visit, or prematurely discontinued the study

2.1.2. Data Monitoring Committee Analysis

An external multidisciplinary Data Monitoring Committee (DMC) reviewed the progress of the study and performed interim reviews of the safety data of a sentinel cohort before opening enrollment of up to a further 20 participants, in order to protect participant welfare and preserve study integrity. To ensure the best interests of the participants, the DMC has made recommendations to the sponsor if the nature, frequency, and severity of adverse effects associated with the study treatment warrant the early termination of the study, the continuation of the study, or the continuation of the study with modifications.

The review was conducted after the 5 participants from the sentinel cohort had completed their Day 21 visit or had prematurely discontinued the study.

The DMC's role and responsibilities and the scope of analysis to be provided to the DMC were provided in a mutually agreed upon charter, which defines the DMC membership, meeting logistics, and meeting frequency.

2.2. Final Analysis

The final analysis will be performed after all participants have completed the study or prematurely terminated from the study, outstanding data queries have been resolved or adjudicated as unresolvable, and the data have been cleaned and finalized.

2.3. Changes From Protocol-Specified Analyses

The second interim analysis was not performed as the last participant's completion of end-of-Period 3 visit occurred late to meet the CROI 2025 conference abstract submission deadline. To ensure timely abstract submission, an ad-hoc analysis was performed instead.

3. GENERAL CONSIDERATIONS FOR DATA ANALYSES

Analysis results will be presented using descriptive statistics. For categorical variables, the number and percentage of participants in each category will be presented; for continuous variables, the number of participants (n), mean, standard deviation (SD) or standard error (SE), median, first quartile (Q1), third quartile (Q3), minimum, and maximum will be presented.

By-participant listings will be presented for all participants in the All Enrolled Analysis Set and sorted by participant ID number in ascending order, visit date, and time (if applicable), unless otherwise specified. Data collected on log forms, such as AEs, will be presented in chronological order within the participant. The treatment group to which participants were initially assigned will be used in the listings. Age, sex at birth, race, and ethnicity will be included in the listings, as space permits.

3.1. Analysis Sets

Analysis sets define the participants to be included in an analysis. Analysis sets and their definitions are provided in this section. The analysis set will be identified and included as a subtitle of each table, figure, and listing.

For each analysis set, the number and percentage of participants eligible for inclusion as well as the number and percentage of participants who were excluded and the reason for their exclusion will be summarized.

A listing of reasons for exclusion from analysis sets will be provided by participant.

3.1.1. All Enrolled Analysis Set

The All Enrolled Analysis Set includes all participants who received a study participant identification number in the study after screening. This is the primary analysis set for by-participant listings.

3.1.2. Full Analysis Set

The Full Analysis Set (FAS) includes all enrolled participants who took at least 1 dose of study drug. This is the primary analysis set for efficacy analyses.

3.1.3. Safety Analysis Set

The Safety Analysis Set includes all participants who took at least 1 dose of study drug. This is the primary analysis set for safety analyses.

3.1.4. Pharmacokinetic Analysis Set

The VES PK Analysis Set includes all enrolled participants who took at least 1 dose of VES and have at least 1 non-missing postdose VES concentration value reported by the PK laboratory.

The VRC07-523LS PK Analysis Set includes all enrolled participants who took at least 1 dose of VRC07-523LS and have at least 1 non-missing postdose VRC07-523LS concentration value reported by the PK laboratory.

The CAP256V2LS PK Analysis Set includes all enrolled participants who took at least 1 dose of CAP256V2LS and have at least 1 non-missing postdose CAP256V2LS concentration value reported by the PK laboratory.

These are the primary analysis sets for all PK analyses.

3.1.5. Immunogenicity Analysis Set

The VRC07-523LS Immunogenicity Analysis Set includes all enrolled participants who took at least 1 dose of VRC07-523LS and have at least 1 non-missing postdose antidrug antibody (ADA) result for immunogenicity evaluation.

The CAP256V2LS Immunogenicity Analysis Set includes all enrolled participants who took at least 1 dose of CAP256V2LS and have at least 1 non-missing postdose ADA result for immunogenicity evaluation.

The VRC07-523LS and CAP256V2LS Immunogenicity Analysis Set includes all enrolled participants who took at least 1 dose of VRC07-523LS and 1 dose of CAP256V2LS and have at least 1 non-missing postdose ADA result for both immunogenicity evaluations.

3.2. Participant Grouping

For analyses based on All Enrolled Analysis Set and FAS, participants will be grouped according to the treatment to which they were enrolled (i.e., VES + VRC + CAP). For analyses based on Safety Analysis Set, PK Analysis Set and Immunogenicity Analysis Set, participants will be grouped according to the actual treatment received.

3.3. Strata and Covariates

This study does not use a stratified randomization schedule when enrolling participants. No covariates will be included in efficacy and safety analyses.

3.4. Examination of Participant Subgroups

There are no prespecified participant subgroupings for efficacy and safety analyses.

3.5. Multiple Comparisons

Adjustments for multiplicity will not be made, because no formal statistical testing will be performed in this study.

3.6. Missing Data and Outliers

3.6.1. Missing Data

In general, missing data will not be imputed unless methods for handling missing data are specified. Exceptions are presented in this document.

The handling of missing or incomplete dates for AE start is described in Section [7.1.6.2](#), and for prior and concomitant medications in Section [7.4.2](#). Missing PK sampling dates may be imputed based on other visit information. Missing PK sampling times may be imputed to nominal times. Missing drug concentrations will not be imputed.

3.6.2. Outliers

Outliers of non-PK data will be identified during the data management and data analysis process, but no sensitivity analyses will be conducted. All data will be included in the data analysis.

Individual study drug concentration values may be identified as outliers by the clinical pharmacokineticist and excluded from concentration summary tables and figures and from the noncompartmental PK analysis. Outlier drug concentrations will be identified in the concentration listing along with the justification for exclusion.

3.7. Data Handling Conventions and Transformations

Only year of birth is collected on the CRF; “01July” will be imputed as the day and month of birth.

In general, age collected at Day 1 (in years) will be used for analyses and presented in listings. If age at Day 1 is not available for a participant, then age derived based on date of birth and the Day 1 visit date will be used instead. If an enrolled participant was not dosed with any study drug, the enrollment date will be used instead of the Day 1 visit date. For screen failures, the date the first informed consent was signed will be used for the age derivation. Age required for longitudinal and temporal calculations and analyses (e.g., estimates of creatinine clearance, age at date of AE) will be based on age derived from date of birth and the date of the measurement or event, unless otherwise specified.

Non-PK data that are continuous in nature but are less than the lower limit of quantitation (LLOQ) or above the upper limit of quantitation (ULOQ) will be imputed as follows:

- A value that is 1 unit less than the LLOQ at the same precision level of the originally reported value will be used to calculate descriptive statistics if the datum is reported in the form of “ $< x$ ” (where x is considered the LLOQ). For example, if the values are reported as < 50 and < 5.0 , values of 49 and 4.9, respectively, will be used to calculate summary statistics. An exception to this rule is any value reported as < 1 or < 0.1 , etc. For values reported as < 1 or < 0.1 , a value of 0.9 or 0.09, respectively, will be used to calculate summary statistics.
- A value that is 1 unit above the ULOQ will be used to calculate descriptive statistics if the datum is reported in the form of “ $> x$ ” (where x is considered the ULOQ). Values with decimal points will follow the same logic as above.
- The lower or ULOQ will be used to calculate descriptive statistics if the datum is reported in the form of “ $\leq x$ ” or “ $\geq x$ ” (where x is considered the lower or upper limit of quantitation (LOQ), respectively).

If methods based on the assumption that the data are normally distributed are not adequate, analyses may be performed on transformed data or nonparametric analysis methods may be used, as appropriate.

Logarithmic (base 10) transformations will be applied to HIV-1 RNA data for efficacy analysis. For analysis purposes, HIV-1 RNA results of “ <20 cp/mL” or not detectable will be imputed as 19 copies/mL, “ <30 cp/mL” will be imputed as 29 copies/mL; “ <100 cp/mL” will be imputed as 99 copies/mL.

Natural logarithm transformation will be used for analyzing not below the limit of quantitation (non-BLQ) concentrations and PK parameters in intensive PK samples. Concentration values that are BLQ will be presented as “BLQ” in the concentration data listing. Values that are BLQ will be treated as 0 at predose and postdose time points for summary purposes. The number of samples will be summarized to reflect the actual number of samples assessed at that time point.

At predose, if all concentration values are BLQ, then the mean, and order statistics (minimum, first quartile [Q1], median, third quartile [Q3], and maximum) will be displayed as 0 and the rest of the summary statistics (i.e., standard deviation [SD] and coefficient of variation [CV]) will be missing. If any values are non-BLQ, then the number of samples, order statistics, and all summary statistics will be displayed.

At any given postdose time point, if more than one-third of the participants have a concentration value of BLQ, then only the number of samples and order statistics will be displayed; otherwise, order statistics and summary statistics will be displayed.

The following conventions will be used for the presentation of order statistics for postdose time points:

- If at least 1 participant has a concentration value of BLQ for the time point, the minimum value will be displayed as “BLQ”.
- If more than 25% of the participants have a concentration data value of BLQ for a given time point, the minimum and Q1 values will be displayed as “BLQ”.
- If more than 50% of the participants have a concentration data value of BLQ for a given time point, the minimum, Q1, and median values will be displayed as “BLQ”.
- If more than 75% of the participants have a concentration data value of BLQ for a given time point, the minimum, Q1, median, and Q3 values will be displayed as “BLQ”.
- If all participants have concentration data values of BLQ for a given time point, all order statistics (minimum, Q1, median, Q3, and maximum) will be displayed as “BLQ”.

Similarly, for PK concentration plots, if more than one-third of the participants have concentration values of BLQ, then the mean and standard deviation are not displayed at that timepoint; and if more than one-half of the participants have concentration values of BLQ, then the median and quartiles are not displayed at that timepoint.

Concentration related PK parameters (e.g., C_{last} , C_{max}) that are BLQ will be excluded before log transformation or statistical model fitting and displayed as described above.

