6.10.1. Virologic Rebound

Virologic rebound is defined as follows:

- At any visit a rebound in HIV-1 RNA to ≥ 50 copies/mL, which is subsequently confirmed at the following scheduled or unscheduled visit

At any visit, if the HIV-1 RNA is ≥ 50 and < 200 copies/mL, a reflex HIV-1 RNA repeat test will be conducted on stored plasma samples, if available. If the repeat result is < 50 copies/mL, no further action is required. If the repeat result is ≥ 50 copies/mL, participants will be asked to return to the clinic for a scheduled or unscheduled blood draw (1 week after the date of the original test that resulted in HIV-1 RNA VR) for confirmation of VR.

A plasma sample from either the first instance or the VR confirmation visit will be tested for resistance to VRC07-523LS, CAP256V2LS, and baseline ART.

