3.8.2. Analysis Visits

The nominal visit as recorded on the eCRF or lab date will be used when data are summarized by visit. Any data relating to unscheduled visits will not be assigned to a particular visit or time point and in general will not be included in by-visit summaries. However, the following exceptions will be made:

- An unscheduled visit prior to the first dose of study drug may be included in the calculation of baseline value, if applicable.
- Unscheduled visits after the first dose of study drug will be included in determining the maximum postbaseline toxicity grade and time to event analyses.
- For participants who prematurely discontinued from the study drug, early termination (ET) data will be summarized as a separate visit, labeled as “Early Study Drug Discontinuation”.
- Data obtained after the follow-up visit or last exposure date (whichever is later) will be excluded from the summaries but will be included in the listings.

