6. EFFICACY ANALYSES

6.1. Definition of Efficacy Endpoints

Efficacy endpoints include the following:

- Time to virologic rebound following ATI based on 2 different cutoff values:
 - 1) ≥ 50 copies/mL
 - 2) ≥ 200 copies/mL
- Change in plasma viral load set-point following ATI
- Time to ART resumption following ATI

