6.3. Analysis of Efficacy Endpoints

The Full Analysis Set will be used for the efficacy endpoint analysis.

Descriptive statistics will be provided for HIV-1 RNA data as follows:

- Baseline HIV-1 RNA value
- Change from baseline in HIV-1 RNA (\log_{10} copies) at each postbaseline visit up to the last exposure date for participants who have permanently discontinued study drug.

The baseline HIV-1 RNA value will be defined as the last measurement obtained on or prior to the date/time of first dose of study drug. Change from baseline to a postbaseline visit will be defined as the visit value minus the baseline value, and summarized using descriptive statistics (n, mean, SD, 95% confidence interval [CI], median, Q1, Q3, minimum, and maximum). The mean, median, Q1, Q3, minimum, and maximum values will be displayed to the reported number of digits; SD values will be displayed to the reported number of digits plus 1. In the case of multiple values in an analysis window, data will be selected for analysis as described in Section 3.8.3. No formal statistical testing is planned.

The change in plasma viral load set-point is defined as the value following ATI minus the pre-ART value. The plasma viral set-point following ATI is calculated as the geometric mean of all the HIV-1 RNA measurements between a specified start and end date. The start date and end date will be provided by the study's clinical development team and clinical virologist based on individual participant data review. The pre-ART set point value is the HIV-RNA load count prior to start of initial ARV treatment recorded in the clinical database. Change in plasma viral load set-point following ATI will be summarized and analyzed in the same fashion as that of the change from baseline in plasma \log_{10} HIV-1 RNA.

A by-participant listing for HIV-1 RNA value will be provided by participant ID number and visit in chronological order.

A figure of individual participant \log_{10} HIV-1 RNA value versus time following ATI will be provided.

Virologic rebound is defined as: at any visit a rebound in HIV-1 RNA to cutoff value, which is subsequently confirmed at the following scheduled or unscheduled visit.

Time to virologic rebound will be analyzed using the Kaplan-Meier method. Participants who do not rebound will be censored at the last HIV-1 RNA collection date during ATI period.

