Time to ART resumption following ATI will be analyzed in the same fashion as that of the time to virologic rebound using the Kaplan-Meier method. Participants who do not resume ART will be censored at the last study date. Participants with ART resumed on or prior to end of Period 3 visit date will be flagged.

The above time-to-event endpoints are defined as the time interval (in weeks) between the ATI start date and the event or censoring date, calculated as $(\text{the event or censoring date} - \text{ATI start date} + 1) / 7$.

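### SAP Section 3.7 turns an HIV-1 RNA result of `<100` copies/mL into 99, and Section 6.3 does not say that rebound at ≥ 50 is scored on reported results

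*SAP*

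**What the plan says.** SAP Section 3.7 contains two rules for results below a quantitation limit that matter here.

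- The general rule for non-PK data is restricted in scope: a value one unit under the limit "at the same precision level of the originally reported value will be used to calculate descriptive statistics".
- The HIV-1 RNA rule comes later, directly after the sentence that applies log10 transformation for efficacy analysis. It sets `<20` or not detectable to 19 and `<30` to 29, and says that `<100` "will be imputed as 99 copies/mL". It is introduced as applying for analysis, with no restriction to summaries.

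SAP Section 6.1 lists "Time to virologic rebound following ATI based on 2 different cutoff values", namely ≥ 50 and ≥ 200 copies/mL. SAP Section 6.3 defines rebound as "at any visit a rebound in HIV-1 RNA to cutoff value, which is subsequently confirmed at the following scheduled or unscheduled visit", analysed by Kaplan-Meier with participants who do not rebound censored at the last HIV-1 RNA collection during the analytical treatment interruption (ATI). On timing: "The above time-to-event endpoints are defined as the time interval (in weeks) between the ATI start date and the event or censoring date". Under SAP Section 3.8.2, unscheduled visits after the first dose "will be included in determining the maximum postbaseline toxicity grade and time to event analyses". Protocol Section 6.10.1 uses the same confirmation rule. For a result from 50 to below 200 whose repeat on stored plasma is also at least 50, it asks for a draw "1 week after the date of the original test that resulted in HIV-1 RNA VR". It does not classify a `<100` result.

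**The concern.** A result reported as `<100` may lie anywhere below 100, so it does not show whether HIV-1 RNA had reached 50. Once it is replaced by 99 it passes the ≥ 50 test. A programmer who carries the imputed variable into the rebound derivation is following Section 3.7 as written. One who uses the reported result is following Section 6.3 as most people would understand it. Both comply with the plan, yet they can derive a different event or event date from the same record.

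Time to rebound at ≥ 50 copies/mL is a listed secondary efficacy endpoint. In an uncontrolled study with at most 25 participants, one event is visible on the curve.

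**Working it through.** **Inputs.** Imputed values and the below-limit rule: SAP Section 3.7. Cutoffs: Section 6.1. Confirmation, censoring and week formula: Section 6.3. ATI start on Day 35 and 2-weekly HIV-1 RNA from Day 42: Protocol Sections 6.4 and 6.4.1. The HIV-1 RNA sequences are assumed, and events are dated at the first of the two samples, which Section 6.3 does not state.

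**Step 1: reproduce the plan's values.** Limit minus one unit: 20 − 1 = 19, 30 − 1 = 29, 100 − 1 = 99. All three agree with Section 3.7.

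**Step 2: compare with the cutoffs.** 19 and 29 are below 50. 99 is at least 50 and below 200. On the log10 scale, 19, 29 and 99 are 1.279, 1.462 and 1.996, against 1.699 for 50. Only `<100` can change status, and only at the 50 cutoff.

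**Step 3: convert days to weeks.** Weeks = (day − 35 + 1)/7. Day 42: 8/7 = 1.14. Day 56: 22/7 = 3.14. Day 70: 36/7 = 5.14.

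**Step 4: score confirmed rebound at ≥ 50.**

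| Days | Assumed results | Imputed values | Reported values, `<100` not counted |
|---|---|---|---|
| 42/56/70/84 | `<20, <100, <100, <20` | Day 56, 3.14 weeks | no event |
| 42/56/63/70 | `<20, 60, <100, <20` | Day 56, 3.14 weeks | no event |
| 42/56/70/84 | `<20, <100, 500, 2000` | Day 56, 3.14 weeks | Day 70, 5.14 weeks |
| 42/56/70/84 | `<20, <100, <20, <20` | no event | no event |

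The second row assumes that the repeat of the 60 on stored plasma is also at least 50 and that the 1-week draw falls on Day 63. If Day 70 were 500 in that row, Day 56 would still be unconfirmed on reported results, because the following visit did not show 50. The earliest event would be Day 70 (5.14 weeks), if later confirmed, against 3.14 weeks on imputed values.

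In the third row the true crossing is interval-censored between Day 42 (1.14 weeks) and Day 70 (5.14 weeks), so neither date is shown to be right. Protocol Section 3.2 describes weekly virus monitoring in Period 2. With samples on Days 42/49/56/63 the same results give 15/7 = 2.14 versus 22/7 = 3.14 weeks.

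Dating events at the confirming sample changes the figures but not the disagreement: the first row becomes 5.14 weeks versus none, and the third 5.14 versus 50/7 = 7.14 weeks.

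At ≥ 200 the two scorings agree in every row: no event in rows one, two and four, and Day 70 in row three.

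**Step 5: effect on the curve.** An event lowers the Kaplan-Meier estimate by S(t−)/n, where n is the number at risk. As the first event among 25, it lowers the curve by 1/25 = 4 percentage points. After 15 events without censoring, S = 10/25 = 0.4 and n = 10, so the drop is 0.4/10 = 4 points again. The number entering ATI is not stated; 25 is the planned maximum.

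**The case against.** The strongest reply is that the imputation was meant only for numerical summaries. It sits among transformations, next to the log10 sentence. Its values are the general rule applied to HIV-1 RNA, and that rule is for descriptive statistics. Numbers are needed for the change-from-baseline tables and the geometric-mean set-point. A result known only to be below 100 does not show a rebound to 50. This reading is plausible and may be what the authors intended, but no section makes it binding. The SAP limits scope elsewhere when it means to, both in the general rule and in the summary-only handling of PK values, and the HIV-1 RNA rule carries no such limit.

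A second reply is that eligibility (Protocol Section 4.2), ATI entry (6.3.3), the weekly-testing trigger (6.6) and rebound (6.10.1) all need results resolved at 50, so an assay with a routine limit of 100 could hardly serve the study. The `<100` rule might then concern only historical values. This stands as a reason to expect few or no such results during ATI. It does not remove the category that Section 3.7 names. The assay requirement in the protocol synopsis can be read as a limit of 50 or lower, or as 50 or higher.

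The remaining limits are accepted. Confirmation is required, so a lone `<100` between results below 50 creates no event. There is no formal testing. An event can also be checked by hand: "A by-participant listing for HIV-1 RNA value will be provided by participant ID number and visit in chronological order".

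**Conclusion.** The point holds as a minor ambiguity with a literal reading that gives the wrong kind of event: a result indeterminate at 50 can start or confirm a ≥ 50 rebound. It takes two consecutive `<100` results, or one next to a value of at least 50. Results of `<20` and `<30`, the ≥ 200 endpoint and the primary safety endpoints are unaffected. The sizes shown rest on assumed sequences and an ATI start on Day 35. The frequency of `<100` during ATI is not given and may be zero.

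A reader might infer more than the documents support:

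- The SAP does not state that 99 is used to score rebound; it only fails to exclude it.
- It is not shown that any reported rebound time is wrong. Section 2.3 mentions an ad hoc analysis but does not say that it scored rebound.
- A larger effect, such as 10 points when 10 are at risk, would require that no event had occurred before then, and nothing in the documents supports that.

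**What to change.** Add to SAP Section 6.3, or document in the clinical study report as SAP Section 1 provides for changes after finalization:

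- the rebound cutoffs are applied to reported HIV-1 RNA results;
- the imputed 99 is used only for descriptive and log10 summaries;
- `<100` is indeterminate at the 50 cutoff, and confirmation at the following scheduled or unscheduled visit stays as it is.

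If any `<100` result occurred during ATI, report time to rebound at ≥ 50 both ways: `<100` not counted, and `<100` counted as at least 50. Otherwise state that none occurred.

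The cost is one or two sentences and at most one extra Kaplan-Meier run, with no new data. The drawback is that the clarification comes late and its main version leans toward a longer time to rebound. It should be labelled as a late clarification, and the two-way report shows how much it matters.
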